7.2.3 Specimen Preparation, Handling, and Storage

[REDACTED]

[REDACTED]

See attached documents (Section 19) for detailed standard operating procedures for specimen processing, collection and shipping instructions from Quest Laboratories, as well as for the accreditation documentation for the Transplant Research Lab, where these specimens will be processed and stored.

7.2.4 Specimen Shipment

Serum samples sent to Quest Laboratories will be shipped frozen, according to collection and shipment instructions from Quest (see attachment in Section 19).

7.3 Study Schedule

7.3.1 Screening

Screening Visit (Day -365 to -1)

- Review medical history and perform physical examination to determine eligibility based on inclusion/exclusion criteria.
- Review medications history to determine eligibility based on inclusion/exclusion criteria.
- Collect blood to ensure that potential subjects have no evidence of current or prior infection with HCV, HBV, or HIV: HCV NAT and serologies, HBV NAT and serologies, HIV.
- Collect blood for documentation of pre-transplant liver function: hematology, biochemistry, coagulation
- Provide participants with detailed information about the study, in particular, conduct a detailed conversation of the risks and benefits of the trial. Risks discussed will include but not be limited to: risks of contracting treatment-resistant HCV and potential consequences of chronic HCV infection. Benefits discussed will include but not be limited to: shortened time to heart transplantation, and minimizing of the chance of death on the waiting list while waiting for a HCV negative organ offer. A Fact Sheet outlining the basic objectives, procedures, risks and benefits will be provided to patients.
- Obtain written acknowledgement of willingness to participate in study and receipt of Fact Sheet.

7.3.2 Enrollment/Baseline

Enrollment/Baseline Visit (Day -1 to 0)

CONFIDENTIAL

This material is the property of the NYU School of Medicine and Langone Medical Center. Do not disclose or use except as authorized in writing by the study sponsor
Interventional Template Version: 28 APR 2017

- Organ offer for a HCV-positive donor heart is received. The donor inclusion criteria are reviewed to ensure all donor criteria are met.
- The organ offer and the opportunity to participate in the trial are discussed with the patient and if the patient accepts, the patient is then admitted to the hospital in preparation for heart transplant.
- Inclusion/exclusion criteria for the recipient are reviewed again
- Written informed consent to participate in the trial is obtained.
- Obtain urine pregnancy test from any woman participant of childbearing age.
- Record vital signs, results of examinations, other assessments.
- Collect blood for baseline hematology, biochemistry coagulation, HCV NAT and serologies, HBV NAT and serologies, and HIV serology.
- Heart transplant operation is performed as per standard of care techniques.
- Donor blood is acquired with the donor organ, and donor serum sent to Quest Laboratories for HCV genotyping (to be performed in parallel with the transplant). Donor serum is banked for repeat testing in the event of indeterminate genotyping results.

7.3.3 Intermediate Visits

For the schedules below, the following time-post-event designations will be used:

POW (Post-operative week) – refers to weeks following the transplant operation

PMW (Post-Mavyret treatment week) – refers to weeks following the initiation of Mavyret therapy

All patients post-transplant will enter the Surveillance Phase which will entail weekly screening for the development of HCV viremia post-transplant for 8 weeks. Time in the surveillance phase is measured in reference to the transplant itself, in POW. Patients who never develop HCV viremia during the Surveillance Phase will transition to the No Transmission schedule detailed below. Time in the No Transmission arm is measured in reference to the transplant itself, in POW.

Patients who develop detectable HCV viremia during the Surveillance Phase will immediately exit the Surveillance Phase and enter the Mavyret Treatment arm schedule as detailed below. Time in the Mayvret Treatment arm is measured in reference to the date that Mavyret treatment was initiated, in PMW.

SURVEILLANCE PHASE SCHEDULE OF EVENTS

POW1 (+/- 1 day)

- In person visit, record vital signs
- Record standard of care labs: hematology, biochemistry, coagulation
- Collect study labs: HCV NAT

POW2 (+/- 2 days)

- In person visit, record vital signs
- Record standard of care labs: hematology, biochemistry, coagulation
- Collect study labs: HCV NAT

POW3 (+/- 3 days)

- Record standard of care labs: hematology, biochemistry, coagulation
- Collect study labs: HCV NAT

POW4 (+/- 5 days)

- In person visit, record vital signs
- Record standard of care labs: hematology, biochemistry, coagulation, HBV serologies and NAT, HIV serologies
- Collect study labs: HCV NAT

CONFIDENTIAL

This material is the property of the NYU School of Medicine and Langone Medical Center. Do not disclose or use except as authorized in writing by the study sponsor

POW5 (+/- 5 days)

- Record standard of care labs: hematology, biochemistry, coagulation
- Collect study labs: HCV NAT

POW6 (+/- 5 days)

- Record standard of care labs: hematology, biochemistry, coagulation
- Collect study labs: HCV NAT

POW7 (+/- 5 days)

- Record standard of care labs: hematology, biochemistry, coagulation
- Collect study labs: HCV NAT

POW8 (+/- 5 days)

- Record vital signs
- Record standard of care labs: hematology, biochemistry, coagulation,
- Collect study labs: HCV NAT and serology

NO TRANSMISSION ARM SCHEDULE OF EVENTS

POW12 (+/- 7 days)

- In person visit, record vital signs
- Record standard of care labs: hematology, biochemistry, coagulation, HBV serologies and NAT, HIV serologies
- Collect study labs: HCV NAT and serology

POW16 (+/- 7 days)

- Record standard of care labs: hematology, biochemistry, coagulation
- Collect study labs: HCV NAT and serology

POW20 (+/- 7 days)

- Record standard of care labs: hematology, biochemistry, coagulation
- Collect study labs: HCV NAT and serology

POW24 (+/- 14 days): INTERIM ASSESSMENT AT 6-months post-transplant

- In person visit, record vital signs
- Record standard of care labs: hematology, biochemistry, coagulation
- Collect study labs: HCV NAT and serology

MAVYRET TREATMENT ARM SCHEDULE OF EVENTS

PMW0 (+/- 5 days of determination of HCV viremia)

- Initiate Mavyret therapy (daily dosing x 8 weeks)
- In person visit, record vital signs

PMW1 (+/- 1 day)

- Record standard of care labs: hematology, biochemistry, coagulation
- Collect study labs: HCV NAT and serology

PMW2 (+/- 2 day)

- Record standard of care labs: hematology, biochemistry, coagulation
- Collect study labs: HCV NAT and serology

PMW3 (+/- 3 day)

- Record standard of care labs: hematology, biochemistry, coagulation

CONFIDENTIAL

This material is the property of the NYU School of Medicine and Langone Medical Center. Do not disclose or use except as authorized in writing by the study sponsor
Interventional Template Version: 28 APR 2017

- Collect study labs: HCV NAT and serology

PMW4 (+/- 5 day)

- In person visit, record vital signs
- Record standard of care labs: hematology, biochemistry, coagulation, HBV serologies and NAT, HIV serologies
- Collect study labs: HCV NAT and serology

PMW5 (+/- 5 day)

- Record standard of care labs: hematology, biochemistry, coagulation
- Collect study labs: HCV NAT and serology

PMW6 (+/- 5 day)

- Record standard of care labs: hematology, biochemistry, coagulation
- Collect study labs: HCV NAT and serology

PMW7 (+/- 5 day)

- Record standard of care labs: hematology, biochemistry, coagulation
- Collect study labs: HCV NAT and serology

PMW8 (+/- 5 day)

- In person visit, record vital signs
- Confirm completion of Mavyret treatment course
- Record standard of care labs: hematology, biochemistry, coagulation
- Collect study labs: HCV NAT and serology

PMW9 (+/- 5 day)

- Record standard of care labs: hematology, biochemistry, coagulation
- Collect study labs: HCV NAT and serology

PMW10 (+/- 5 day)

- Record standard of care labs: hematology, biochemistry, coagulation
- Collect study labs: HCV NAT and serology

PMW11 (+/- 5 day)

- Record standard of care labs: hematology, biochemistry, coagulation
- Collect study labs: HCV NAT and serology

PMW12 (+/- 5 day)

- Record standard of care labs: hematology, biochemistry, coagulation
- Collect study labs: HCV NAT and serology

PMW16 (+/- 5 day)

- Record standard of care labs: hematology, biochemistry, coagulation
- Collect study labs: HCV NAT and serology

POW24 (+/- 14 days): INTERIM ASSESSMENT AT 6-months post-transplant

- In person visit, record vital signs
- Record standard of care labs: hematology, biochemistry, coagulation
- Collect study labs: HCV NAT and serology

7.3.4 Final Study Visit - for all patients

CONFIDENTIAL

This material is the property of the NYU School of Medicine and Langone Medical Center. Do not disclose or use except as authorized in writing by the study sponsor
Interventional Template Version: 28 APR 2017

POW52 (+/- 14 days): FINAL ASSESSMENT AT 12-months post-transplant

- In person visit, record vital signs
- Record standard of care labs: hematology, biochemistry, coagulation, HBV serologies and NAT, HIV serologies
- Collect study labs: HCV NAT and serology

7.3.5 Withdrawal/Early Termination Visit

Early withdrawal will be strongly discouraged for patients and the need to complete the entire follow-up course will be discussed with patients prior to enrolling in the study. Concern for the ability to follow-up will constitute exclusion from entry into the study.

For patients who do not develop HCV viremia post-transplant early withdrawal from the study will mean incomplete surveillance for the possible development of HCV. The importance of this screening will be discussed in detail with any person who elects to discontinue the follow-up.

Patients who develop HCV viremia and begin treatment, who elect to terminate treatment prior to the completion of the course will be counseled that this constitutes a risk for the development of chronic HCV and potential liver disease and/or liver failure in the future. Patients who elect to terminate therapy will be referred to a hepatologist for long-term follow-up and surveillance after HCV infection/exposure.

In general, we do not anticipate that there will be any withdrawal or early termination from the patients who enroll in this study. Because these patients will have had a heart transplant and maintaining a heart transplant generally requires close follow-up both for monitoring of graft function and for monitoring of immunosuppression, in general this is a very low risk group of patients to be lost to follow-up.

7.3.6 Unscheduled Visit

Patients who undergo heart transplantation are expected to have a need for unscheduled visits depending on their clinical course. Unscheduled visits that pertain directly to the trial (i.e. due to reactions or intolerances to Mavyret, due to illness associated with acute HCV infection, HCV resistances) will occur as clinically appropriate and any AEs/SAEs will be documented as described below.

7.4 Concomitant Medications, Treatments, and Procedures

The subjects will receive concomitant medications which would otherwise be given as standard of care for patients undergoing a heart transplant.

All concomitant prescription medications taken during study participation will be recorded on the case report forms (CRFs). For this protocol, a prescription medication is defined as a medication that can be prescribed only by a properly authorized/licensed clinician. Medications to be reported in the CRF are concomitant prescription medications, over-the-counter medications and non-prescription medications.

7.4.1 Precautionary Medications, Treatments, and Procedures

Treatment with amiodarone, digoxin, atorvastatin, lovastatin, simvastatin, pravastatin, rosuvastatin, flucastatin, pitavastatin requires special consideration and possible dosing adjustments in patients receiving Mavyret and the use of these medications will be discussed by the study team and any dose adjustment plan documented in the CRF.

7.5 Prohibited Medications, Treatments, and Procedures

Treatment with atazanavir, darunavir, lopinavir, ritonavir, efavirenz, rifampin, cyclosporine, ethinyl estradiol-containing oral contraceptives, carbamazepine, dabigatran, St. John's wort will not be permitted.

CONFIDENTIAL

This material is the property of the NYU School of Medicine and Langone Medical Center. Do not disclose or use except as authorized in writing by the study sponsor

7.6 Rescue Medications, Treatments, and Procedures

In the event that a subject fails to achieve SVR with Mavyret, rescue therapy with other marketed agents approved for the treatment of HCV will be administered. The rescue treatment will be determined based on genotyping and resistance testing, and the choice of drug(s) used will be prescribed under the direction of a transplant hepatologist and/or transplant infectious diseases physician.

7.7 Participant Access to Study Agent at Study Closure

Not applicable

8 Assessment of Safety

8.1 Specification of Safety Parameters

8.1.1 Definition of Adverse Events (AE)

An **adverse event** (AE) is any symptom, sign, illness or experience that develops or worsens in severity during the course of the study. Intercurrent illnesses or injuries should be regarded as adverse events. Abnormal results of diagnostic procedures are considered to be adverse events if the abnormality:

- results in study withdrawal
- is associated with a serious adverse event
- is associated with clinical signs or symptoms
- leads to additional treatment or to further diagnostic tests
- is considered by the investigator to be of clinical significance

8.1.2 Definition of Serious Adverse Events (SAE)

Serious Adverse Event

Adverse events are classified as serious or non-serious. A **serious adverse event** is any AE that is:

- fatal
- life-threatening
- requires or prolongs hospital stay
- results in persistent or significant disability or incapacity
- a congenital anomaly or birth defect
- an important medical event

Important medical events are those that may not be immediately life threatening, but are clearly of major clinical significance. They may jeopardize the subject, and may require intervention to prevent one of the other serious outcomes noted above. For example, drug overdose or abuse, a seizure that did not result in in-patient hospitalization, or intensive treatment of bronchospasm in an emergency department would typically be considered serious.

All adverse events that do not meet any of the criteria for serious should be regarded as **non-serious adverse events**.

8.1.3 Definition of Unanticipated Problems (UP)

Unanticipated Problems Involving Risk to Subjects or Others

Any incident, experience, or outcome that meets all of the following criteria:

- Unexpected in nature, severity, or frequency (i.e. not described in study-related documents such as the IRB-approved protocol or consent form, the investigators brochure, etc.)

CONFIDENTIAL

This material is the property of the NYU School of Medicine and Langone Medical Center. Do not disclose or use except as authorized in writing by the study sponsor
Interventional Template Version: 28 APR 2017

- Related or possibly related to participation in the research (i.e. possibly related means there is a reasonable possibility that the incident experience, or outcome may have been caused by the procedures involved in the research)
- Suggests that the research places subjects or others at greater risk of harm (including physical, psychological, economic, or social harm).

8.2 Classification of an Adverse Event

8.2.1 Severity of Event

For AEs not included in the protocol defined grading system, the following guidelines will be used to describe severity.

- **Mild** – Events require minimal or no treatment and do not interfere with the participant's daily activities.
- **Moderate** – Events result in a low level of inconvenience or concern with the therapeutic measures. Moderate events may cause some interference with functioning.
- **Severe** – Events interrupt a participant's usual daily activity and may require systemic drug therapy or other treatment. Severe events are usually potentially life-threatening or incapacitating.

8.2.2 Relationship to Study Agent

The clinician's assessment of an AE's relationship to study is part of the documentation process, but it is not a factor in determining what is or is not reported in the study. If there is any doubt as to whether a clinical observation is an AE, the event should be reported. All AEs must have their relationship to study agent assessed. In a clinical trial, the study product must always be suspect. To help assess, the following guidelines are used.

- **Related** – The AE is known to occur with the study agent, there is a reasonable possibility that the study agent caused the AE, or there is a temporal relationship between the study agent and event. Reasonable possibility means that there is evidence to suggest a causal relationship between the study agent and the AE.
- **Not Related** – There is not a reasonable possibility that the administration of the study agent caused the event, there is no temporal relationship between the study agent and event onset, or an alternate etiology has been established.

For all collected AEs, the clinician who examines and evaluates the participant will determine the AE's causality based on temporal relationship and his/her clinical judgment. The degree of certainty about causality will be graded using the categories below.

- **Definitely Related** – There is clear evidence to suggest a causal relationship, and other possible contributing factors can be ruled out. The clinical event, including an abnormal laboratory test result, occurs in a plausible time relationship to drug administration and cannot be explained by concurrent disease or other drugs or chemicals. The response to withdrawal of the drug (dechallenge) should be clinically plausible. The event must be pharmacologically or phenomenologically definitive, with use of a satisfactory rechallenge procedure if necessary.
- **Probably Related** – There is evidence to suggest a causal relationship, and the influence of other factors is unlikely. The clinical event, including an abnormal laboratory test result, occurs within a reasonable time after administration of the drug, is unlikely to be attributed to concurrent disease or other drugs or chemicals, and follows a clinically reasonable response on withdrawal (dechallenge). Rechallenge information is not required to fulfill this definition.
- **Possibly Related** – There is some evidence to suggest a causal relationship (e.g., the event occurred within a reasonable time after administration of the trial medication). However, other

CONFIDENTIAL

This material is the property of the NYU School of Medicine and Langone Medical Center. Do not disclose or use except as authorized in writing by the study sponsor

factors may have contributed to the event (e.g., the participant's clinical condition, other concomitant events). Although an AE may rate only as "possibly related" soon after discovery, it can be flagged as requiring more information and later be upgraded to "probably related" or "definitely related," as appropriate.

- **Unlikely to be related** – A clinical event, including an abnormal laboratory test result, whose temporal relationship to drug administration makes a causal relationship improbable (e.g., the event did not occur within a reasonable time after administration of the trial medication) and in which other drugs or chemicals or underlying disease provides plausible explanations (e.g., the participant's clinical condition, other concomitant treatments).
- **Not Related** – The AE is completely independent of study drug administration, and/or evidence exists that the event is definitely related to another etiology. There must be an alternative, definitive etiology documented by the clinician.

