Participant Duration	One year
Duration of IP administration	Eight weeks
Population	Adult patients active on the UNOS waiting list for a heart transplant
Study Sites	Single center (NYU Langone Hospital)
Number of participants	Ten patients
Description of Study Agent/Procedure	The heart transplantation will be performed per standard of care techniques, and all post-transplant management of the transplanted organ, including immunosuppression, will be carried out per standard of care. The study-specific interventions will be surveillance for the development of hepatitis C viremia post-transplant, the treatment of viremia with an FDA-approved drug, and then surveillance for sustained virologic response post-treatment.
Reference Therapy	Not applicable
Key Procedures	Monitoring for transmission of hepatitis C after heart transplant, treatment of viremia if it develops, and monitoring for response to treatment.
Statistical Analysis	In this small pilot study, descriptive statistics will be used.

CONFIDENTIAL

This material is the property of the NYU School of Medicine and Langone Medical Center. Do not disclose or use except as authorized in writing by the study sponsor

Interventional Template Version: 05 JAN 2017

Schematic of Study Design

CONFIDENTIAL

This material is the property of the NYU School of Medicine and Langone Medical Center. Do not disclose or use except as authorized in writing by the study sponsor
Interventional Template Version: 28 APR 2017

1 Key Roles

Principal Investigator

[name]
Associate Professor of Medicine
Clinical Director, Heart Failure Program
Medical Director, Heart Transplant and Ventricular Assist Device Program
The Leon H. Charney Division of Cardiology, NYU Langone Health
[name]
[REDACTED]
[REDACTED]

Co-Investigators:

[name]
Professor of Surgery
Surgical Director, Heart Transplantation and Mechanical Circulatory Support
NYU Langone Cardiothoracic Surgery Associates
[name]
[name]
[REDACTED]
[REDACTED]

[name] PhD
Assistant Professor of Surgery
Vice Chair for Research, NYU Langone Transplant Institute
[name],
[name]
[REDACTED]
[REDACTED]

[name]
Professor of Medicine
Director, Hepatology
NYU Langone Hepatology Associates
[name]
[name]
[REDACTED]
[REDACTED]

[name]
Associate Director of VAD and Heart Transplant
NYU Langone Cardiothoracic Surgery Associates
[name]

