7.1.2 Standard of Care Study Procedures

Heart transplantation and all associated procedures will be considered standard of care including: the transplant procedure itself and requisite intra-operative procedures and hemodynamic monitoring, post-operative ICU-level care, inpatient hospital unit care, outpatient post-operative care including, standard induction and maintenance immunosuppression, and standard post-transplant anti-infectious prophylaxis (anti-fungal, anti-pneumocystis, and anti-CMV prophylaxis).

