8.2.3 Expectedness

The Principal Investigator will be responsible for determining whether an AE is expected or unexpected. An AE will be considered unexpected if the nature, severity, or frequency of the event is not consistent with the risk information previously described for the study agent.

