8.3 Time Period and Frequency for Event Assessment and Follow-Up

The occurrence of an AE or SAE may come to the attention of study personnel during study visits and interviews of a study participant presenting for medical care, or upon review by the DSMB. All AEs including local and systemic reactions not meeting the criteria for SAEs will be captured on the appropriate CRF. Information to be collected includes event description, time of onset, clinician's assessment of severity, relationship to study product (assessed only by those with the training and authority to make a diagnosis), and time of resolution/stabilization of the event. All AEs occurring while on study must be documented appropriately regardless of relationship. All AEs will be followed to adequate resolution.

Any medical condition that is present at the time that the participant is screened will be considered as baseline and not reported as an AE. However, if the study participant's condition deteriorates at any time during the study, it will be recorded as an AE. UPs will be recorded in the data collection system throughout the study.

Changes in the severity of an AE will be documented to allow an assessment of the duration of the event at each level of severity to be performed. AEs characterized as intermittent require documentation of onset and duration of each episode.

The PI will record all reportable events with start dates occurring any time after informed consent is obtained until 7 (for non-serious AEs) or 30 days (for SAEs) after the last day of study participation. At each study visit, the investigator will inquire about the occurrence of AE/SAEs since the last visit. Events will be followed for outcome information until resolution or stabilization.

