8.5 Study Halting Rules

Further enrollment of study subjects will be halted under the following conditions:

- Any patient death occurs and is deemed related to the intervention
- Any SAE deemed related to acute HCV infection occurs
- Any SAE deemed related to Mavyret occurs

The PI will inform the IRB and the DSMB within 24 hours of any of these events. The DSMB and study team will convene an emergency meeting as described below. The DSMB will provide recommendations for proceeding with any further enrollment. Patients who are already enrolled and receiving Mavyret treatment will continue to receive treatment unless the DSMB determines that an alternate course of therapy should be pursued for already-enrolled subjects.

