By signing this form, I acknowledge that I have been informed that participation in the above study may be an option for me. The potential risks and benefits of this study have been explained to me and I have received a copy of the HCV Heart Research Study Fact Sheet.

Signing this form does not guarantee that I will be enrolled in this study.

Signing this form does not mean that I cannot receive a heart transplant at NYU Langone outside of this study.

Signing this form designates that if a suitable organ offer from an HCV positive heart donor becomes available, I would like to be contacted and offered enrollment in the study.

Name of Patient (Print) _____ Signature of Patient _____ Date _____

Name of Person Providing this Form (Print) _____ Signature of Person Providing this Form _____ Date _____

CONFIDENTIAL

This material is the property of the NYU School of Medicine and Langone Medical Center. Do not disclose or use except as authorized in writing by the study sponsor
Interventional Template Version: 28 APR 2017

20 Schedule of Events

For patients who do not develop HCV viremia during the surveillance phase, the following schedule will apply for the entire course of the study:

Activity	Screening visit (Day -365 to -1)	Enrollment visit (Day -1 to 0)	SURVEILLANCE PHASE			
			POW1 (+/- 1 day)	POW2 (+/- 2 day)	POW3 (+/- 3 day)	POW4 (+/- 5 day)
Study team procedures						
Acknowledgement of willingness to participate, provision of Study Fact Sheet	X					
Medical History	X					
Physical Exam	X	X	X	X		
Height	X	X	X	X		X
Weight	X	X	X	X		X
Vitals signs	X	X	X	X		X
Review all donor and recipient inclusion/exclusion criteria		X				
Signing of informed consent		X				
Study specific interventions						
Heart transplant operation		X				
Initiate Mavyret treatment						
Study specific laboratory tests						
Donor serum HCV genotyping		X				
Recipient serum HCV genotyping						
HCV NAT (PCR)	X	X	X	X	X	X
HCV serology (HCV Ab)	X	X				
SOC laboratory tests						
Biochemistry (Na, K, CO2, BUN, Cr, total bili, AST, ALT, alk phos)	X	X	X	X	X	X
Hematology (WBC with ANC, HGB, PLT)	X	X	X	X	X	X
Coagulation (INR)	X	X	X	X	X	X
Urine pregnancy test		X				
HBV NAT (PCR)	X	X				
HBV serology (HBsAb, HBsAg, HBcoreAb)	X	X				
HIV serology (HIV1/2 antigen/antibody 4 th gen)	X	X				

CONFIDENTIAL

This material is the property of the NYU School of Medicine and Langone Medical Center. Do not disclose or use except as authorized in writing by the study sponsor

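### Adverse-event causality and expectedness are defined against Mavyret alone, while the safety rules turn on a study intervention that is never consistently defined

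*Protocol*

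**What the plan says.** Protocol 3.1 makes the safety of the HCV-positive donor heart strategy part of the primary objective, with anti-HCV therapy as the follow-on treatment.

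Three sections judge events against the drug alone:
- **8.2.2, causality.** "All AEs must have their relationship to study agent assessed". On the graded scale, an event is Not Related when "The AE is completely independent of study drug administration" or when another cause is established. The two-level definition also makes an established alternative cause a ground for Not Related.
- **8.3, data captured.** The item is "relationship to study product (assessed only by those with the training and authority to make a diagnosis").
- **8.2.3, expectedness.** An AE is unexpected if its nature, severity or frequency "is not consistent with the risk information previously described for the study agent".

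Sections 8.4.1, 8.4.2, 8.5 and 8.6 refer instead to the study intervention(s), and no section defines the term for that purpose. Three places bear on it:
- The Protocol Summary: "The study-specific interventions will be surveillance for the development of hepatitis C viremia post-transplant, the treatment of viremia with an FDA-approved drug", followed by surveillance for response.
- Section 7.1.2: "Heart transplantation and all associated procedures will be considered standard of care".
- The Section 20 Schedule of Events, which lists "Heart transplant operation" under its heading for study-specific interventions.

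**The concern.** The grading scale answers whether Mavyret caused an event. The objective asks whether the HCV-positive heart did. About 3 in 10 recipients are expected never to take Mavyret, and every recipient has a period after surgery with no drug. For events in those periods the scale has only one natural answer, and a proven donor-derived cause counts as grounds for Not Related.

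This matters because 8.4.1 uses the grades of 8.2.2 (definitely, probably) to decide what is reported quickly, and the Protocol gives no other scale for judging relation to the study intervention. Two investigators could grade the same event differently and both be following the text. A table of related events would then describe the drug and say little about the strategy.

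**Working it through.** The point is mainly one of wording, so the check is to trace an event through the rules.

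**1. A donor-derived HBV or HIV infection.** Section 7.2.1 has recipients tested for both because every HCV-positive donor counts as increased infectious risk. Take a recipient who never becomes viremic and has such an infection, shown to come from the donor and not fatal. No Mavyret was given and another cause is established, so both scales in 8.2.2 lead to Not Related. In a recipient on Mavyret the two-level wording could go either way: timing alone can make an event related, and an established other cause makes it not related.

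**2. What follows from the grade.**

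| Rule | Condition | If graded Not Related | If judged related to the study intervention |
|---|---|---|---|
| 8.4.2, SAE | unexpected and related | IRB and DSMB in 3 days | 24 hours, if unexpected |
| 8.4.1, AE | definitely or probably related | quarterly DSMB and annual IRB review | 3 days |
| 8.6, emergency meeting | unexpected related SAE, or serious related unanticipated problem | none | within one business day |
| 8.5, non-fatal triggers | SAE related to acute HCV or to Mavyret | not covered | not covered, since neither named cause applies |

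For an SAE the reporting difference is 3 days minus 24 hours, or 2 days. For a non-serious AE it is 3 days against the next quarterly meeting. The last row is a gap in 8.5 itself; better grading would not close it.

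**3. An AE from acute HCV before the drug starts.** On the drug-only scale it is Not Related. If study interventions is read as in the Summary, 8.4.1 sends it to quarterly review. Section 10.4.4 requires any AE related to acute HCV to go to the monitoring committee (taken here to be the DSMB) within 3 days. The 8.3 item does not ask about attribution to HCV, so nothing there identifies the events to which 10.4.4 applies.

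**4. Deaths.** Section 8.5 halts enrolment when "Any patient death occurs and is deemed related to the intervention". Section 10.4.7.1 halts it on any death and then assesses relation to HCV exposure, infection or treatment. The two do not agree.

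**5. Expectedness.** A donor-heart harm that is absent from Mavyret's risk information is unexpected under 8.2.3, which favours fast reporting. The step that can block the 24-hour route is therefore relatedness.

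**6. Exposure, as context.** Inputs: N = 10 and 70% viremia (10.5), 8 weeks of drug (6.1.8), 12 months of participation (5.5), taken as 52 weeks.
- Treated: 10 × 0.70 = 7, which reproduces the figure in 10.5. Untreated: 3.
- On-drug time: 7 × 8 = 56 patient-weeks of 10 × 52 = 520, or 10.8%.
- With the N = 20 of 5.6: 14 × 8 = 112 of 1,040, again 10.8%, with 6 untreated.
- With the two-thirds viremia rate of 2.1: about 10.3%.

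**The case against.** A reader might infer that causality is judged only against Mavyret throughout, and that harms of the donor heart therefore escape the safety rules. The documents do not support that:
- Sections 8.4.1 and 8.4.2 have the investigator note the relation of every AE and SAE to the study interventions, and 8.1.3 judges unanticipated problems against participation in the research.
- Acute HCV, the main harm specific to the strategy, has its own halting rule (8.5) and reporting rule (10.4.4). Any death halts enrolment under 10.4.7.1.
- All AEs are recorded whatever their grade (8.2.2, 8.3). SAEs judged unrelated still reach the IRB and DSMB within 3 days, and the DSMB reviews cumulative safety data quarterly (8.6).
- Donor-derived HBV or HIV may qualify as an unanticipated problem, which goes to the IRB within 3 days with the DSMB notified (8.4.3). Section 5.8 allows suspension for unacceptable risk, and 5.2 excludes donors with confirmed HIV or active HBV.
- The graded Not Related category requires the other cause to be documented, so the donor origin would be on record.
- The CRF and the DSMB charter are not in the documents and may say more.

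All of this stands, and it narrows the point. It does not supply a scale for relation to the donor heart or settle what the study intervention is. The unanticipated-problem route to an emergency meeting also requires relation to that undefined intervention.

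**Conclusion.** The concern holds in a limited form. The only defined causality scale, the AE item in 8.3 and the expectedness test refer to Mavyret, while the objective concerns the donor heart and the operational rules use a term the Protocol describes inconsistently. The exposed case is a non-fatal donor-derived harm that is neither acute HCV nor a Mavyret reaction. Graded Not Related, it reaches the DSMB 2 days later if serious, or at quarterly instead of 3-day review if not, and prompts no emergency meeting. It is also outside the triggers in 8.5. Separately, 8.4.1 conflicts with 10.4.4 on HCV-related AEs, and 8.5 conflicts with 10.4.7.1 on deaths.

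A reader might take the 10.8% on-drug share to mean that about 89% of follow-up is unmonitored, or that most events would be misgraded. It shows neither. It is a share of patient-time, assuming 70% viremia, full courses and complete follow-up, and it does not count missed events. The documents give no rate for donor-derived infections other than HCV, so the number of events affected cannot be estimated.

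This should be fixed, preferably before enrolment, because attribution is recorded as events occur.

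**What to change.** - In 8.2.2, 8.3 and the AE/SAE CRF, record two attributions per event: (a) the HCV-positive donor heart or donor-derived infection, and (b) Mavyret.
- In 8.2.3, judge expectedness against the risks stated for both in 2.4.1.
- Define study intervention once, saying whether the HCV-positive donor heart is included, and make the Summary, 7.1.2 and the Section 20 table agree.
- State which attribution each rule in 8.4 to 8.6 uses.
- Reconcile 8.4.1 with 10.4.4, and 8.5 with 10.4.7.1. Which halting rule should apply is for the sponsor and the DSMB to decide.
- In 10.4.4, report AE and SAE counts by each attribution.

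The cost is one extra CRF field and wording changes across several sections. Somewhat more events will be coded related and sent to the DSMB. Attribution to the donor heart will sometimes be hard to separate from ordinary post-transplant complications, especially in a small uncontrolled study. One side effect needs checking: HCV events described in 2.4.1 could become expected and leave the 24-hour route of 8.4.2, so they would depend on the HCV-specific rules in 8.5 and 10.4.4.
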